5. GENERAL ANALYSIS CONSIDERATIONS

The statistical analyses will be reported using summary tables, figures and listings (TFLs). Unless otherwise noted, all statistical testing will be two-sided and will be performed at the 0.05 level of significance.

- Continuous variables will be summarized with the number of non-missing values, estimated means, standard deviations, medians, 25th and 75th percentiles, and observed minimum and maximum values.
- Categorical variables will be summarized by counts and by percentages. The percentage of patients within a category will be displayed in parentheses rounded to the nearest tenth of one percent. However, when the number of patients within a category is 0, then the percentage (i.e., 0.0%) will be omitted.
- Time-to-event variables will be summarized by KM estimates of quartiles, observed minimum and maximum values, and the number of censored observations. The hazard will be estimated by the sum of all individual follow-up times in days divided by 365.25.

Any durations of time expressed in months will be reported in proportional “months” according to the formula

$$\text{months} = \frac{365.25}{12} \text{ days.}$$

Summary tables will be presented by treatment group. Individual subject data will be presented in data listings.

The analyses described in this plan are considered *a priori*, in that they have been defined prior to database lock and prior to breaking the treatment blind. If any *a posteriori* analyses (i.e., analyses not included in this SAP) are performed, they will be identified as such in the CSR where the objective and rationale for executing any *a posteriori* analyses will be documented.

5.1. Analysis Software

In general, data analyses and tabulations will be executed using SAS[®] version 9.2 or higher. SAS[®] programming statements will be validated by an independent programmer and SAS[®] output will undergo a senior-level statistical review to confirm that all data manipulations and calculations are accurate and statistically valid methods have been implemented. Checks will be made to ensure accuracy and consistency with this plan and within and between TFLs. Upon

completion of validation and quality-review procedures, all documentation will be collected and filed by the project statistician or designee.

5.2. Baseline Values

Unless otherwise noted, baseline is defined as the last non-missing value recorded prior to the first dose of study drug. Therefore, data collected during any unscheduled visits will be used in the determination of baseline values, as applicable.

5.3. Missing Values

No imputations will be made for missing values. Summaries will be based on observed data only.

5.4. Subgroup Analyses

Plans for analyses of subgroups based on the presence or absence of anti-tarextumab antibodies are presented in section 11.7 below.

No analyses by baseline characteristics or study center are planned.

Subgroup analyses by baseline Notch3, Hes1, Hey2, Hey1 and Hes6 expression levels are not planned, but the impact these potentially important covariates have on the efficacy of tarextumab will be assessed through statistical modeling (see sections 8.1, 8.3, 8.6 and 8.7).

5.5. Multiple Comparisons/Multiplicity

A gamma(-12) spending function will be used to control the type-1 error for the assessment of efficacy and a gamma(-4) spending function will be used to control the type-1 error for harm arising from multiple analyses of PFS (see Table 1). The same spending functions will be used to control for multiplicity when testing OS (see Table 5).

An additional data filtering rule specific to analyses of PFS and DOR is that deaths reported on the Death Report CRF and AE CRF where death is reported after the cut off date will not be considered.

Additional data filtering rules specific to analyses of OS are:

1. Death reported on Death Report CRF and AE CRF (end date of AE), regardless of date will be included in OS analyses. That is deaths reported after the cutoff date will not be filtered.
2. If the date of death reported on the Death Report CRF and an AE CRF is not the same, the date of death reported on the Death Report CRF will be used. SynteractHCR will notify the sponsor of the discrepancy.
3. The Follow-Up Discontinuation CRF does not explicitly collect date of death. The form only collects the Date of Survival Assessment and Last Known Survival Date. If a patient’s death is reported only on the Follow-Up Discontinuation CRF, then SynteractHCR will notify the sponsor, and the sponsor will advise SynteractHCR how to proceed.

Upon request, a listing of death dates can be generated to show which patients have died and which CRF page was used to acquire the death date.

The planned data cut for the final analysis of OS will be 6 months after the data cut for PFS or when 98 deaths have been observed, whichever occurs first. Once again, the actual data cut for the final formal analysis of OS may be extended beyond 6 months after the PFS data cut for reasons concerning study conduct.

6.1. Analysis Populations

The following five groups of study patients will be used for statistical analyses.

1. The ITT patient population includes all patients randomized to receive study drug regardless of whether they actually received study drug and regardless of whether evidence is found indicating they failed to meet study inclusion/exclusion criteria or had other protocol violations. When the ITT patient population is analyzed, patients are grouped according to

their randomized treatment regardless of actual treatment received. The ITT patient population is the analysis population for demographics and baseline characteristics and for all statistical inference and primary tests of hypotheses related to efficacy endpoints.

2. The safety patient population is the subset of ITT patients who received at least one dose of study drug. When the safety patient population is analyzed, patients are grouped according to actual treatment received. Tarextumab is considered a patient's "treatment received" in the safety patient population if the patient received at least one dose of tarextumab (complete or incomplete dose) any time during the study. The safety patient population is the analysis population for all analyses of safety data.
3. The per-protocol (PP) patient population is the subset of safety patients who either (a) have at least one response evaluation on study, or (b) die prior to their first scheduled response evaluation. When the per-protocol patient population is analyzed, patients are grouped according to actual treatment received. The per-protocol population is used for sensitivity (secondary, supportive) analyses of efficacy endpoints.
4. The pharmacokinetic (PK) patient population is comprised of all subjects who received at least one complete dose of tarextumab and have at least one post-dose PK sample.
5. The immunogenicity patient population is comprised of all subjects who had a baseline and one or more follow-up samples obtained for quantifying anti-tarextumab antibody.

7. SUMMARIES OF PATIENT CHARACTERISTICS

7.1. Subject Disposition

Subject disposition information will be summarized for all subjects by treatment arm. Summaries will include the number of subjects randomized, the number of subjects in each analysis population, the primary reason for stopping each study drug (randomized treatment [tarextumab or placebo], selected platinum therapy [cisplatin or carboplatin] and etoposide), and the primary reason for withdrawing from the study.

The physician's choice of platinum therapy (cisplatin or carboplatin) was used as a stratification variable by the dynamic randomization system. The actual platinum received (as documented on earliest Platinum Therapy Infusion CRF [e.g., Cycle 1, Day 1]) will be summarized in a 2x2 frequency table against the platinum-therapy strata under which a patient was randomized.

7.2. Protocol Deviations

Protocol deviations will be collected and provided by the sponsor. Major protocol deviations that could potentially affect the integrity of efficacy/safety analysis results will be identified prior to database lock and categorized. Major protocol deviations categories may include, but are not limited to enrollment violations, dosing violations, prohibited concomitant therapy violations, and continuation of therapy when treatment should have been discontinued. Major protocol deviations will be summarized by deviation category and treatment group.

7.3. Demographics and Baseline Characteristics

Demographic variables include age, sex, child-bearing potential for females, ethnicity and race. Age will be calculated in years relative to the informed consent date. Baseline characteristics include height, weight, body mass index (BMI), smoking history and Eastern Cooperative

Oncology Group (ECOG) performance status. Descriptive statistics will be presented for age, height and weight; and frequency counts and percentages will be presented for sex, child-bearing potential, ethnicity, race, smoking history (never smoked, ex-smoker, or current smoker) and ECOG performance status. Demographic and baseline characteristics will be summarized for the ITT, safety, PP and immunogenicity populations.

ES-SCLC history, including time since ES-SCLC diagnosis, histological/cytological type (small cell only, mixed type, or other), anatomical location of primary tumor, and number of disease sites (1, 2 or ≥ 3) at study entry will be summarized by treatment group for the ITT and safety populations. The time from ES-SCLC diagnosis to randomization will be quantified in months according to the formula shown in section 5. Summary statistics for baseline values of total tumor length (abbreviated SLD for sum of longest diameters) will be included in the analyses of efficacy endpoints.

Baseline levels of Notch3, Hes1, Hey2, Hey1 and Hes6 will be summarized as a continuous variable in the ITT, safety and per-protocol populations.

Prior therapies (surgeries and radiotherapies) for ES-SCLC will be summarized for the ITT and safety populations.

Patients' medical and surgical histories will be displayed in a data listing.

8. EFFICACY ENDPOINTS

Primary analyses of efficacy endpoints will use data from the ITT population. Additional efficacy analyses will be performed using data from only the PP population, but these analyses are considered secondary.

Efficacy endpoints include investigator-assessed PFS, assessment of SLD as a continuous variable, ORR defined as the proportion of patients achieving a CR or PR, duration of response (DOR), sites of progression, OS and landmark survival at 180, 360, 540 and 720 days.

As mentioned in section 5 above,

- Continuous variables will be summarized with the number of non-missing values, estimated means, standard deviations, medians, 25th and 75th percentiles, and observed minimum and maximum values.
- Categorical variables will be summarized by counts and by percentages. The percentage of patients within a category will be displayed in parentheses rounded to the nearest tenth of one percent. However, when the number of patients within a category is 0, then the percentage (i.e., 0.0%) will be omitted.
- Time-to-event variables will be summarized by KM estimates of quartiles, observed minimum and maximum values, and the number of censored observations. The hazard will be estimated by the sum of all individual follow-up times in days divided by 365.25.

8.1. Progression-Free Survival

On study tumor assessments are those that meet the following criteria:

1. No gap of >91 days between successive tumor assessments among those on or prior to the on study tumor assessment. (Note: a tumor assessment for which “Not Evaluated” is entered into the database does not qualify as a tumor assessment.)
2. No prior initiation of non-protocol anticancer therapy.

PFS, the primary endpoint of the study, is defined as the time from randomization (Day 1) until the first occurrence of death or disease progression based on investigator assessments of tumor response per the RECIST criteria. Progressions that are not determined from on study tumor assessments as well as deaths occurring more than 49 days from the last on-study tumor assessment are not treated as progression events. Subjects without a progression event will be censored at their last on study tumor assessment.

In addition two special cases will be handled in a manner consistent with the above rules as follows:

1. Patients whose first tumor assessment is >91 days from randomization will be censored on the date of randomization with a PFS of 1 day.
2. Patients who never had an on study tumor assessment and who did not die within 49 days (the scheduled time between tumor assessments plus 7 days) after randomization will be censored on the date of randomization with a PFS of 1 day.

The KM method will be used to estimate the proportions of subjects over time without progression or death and the median progression-free survival time. KM curves will be plotted by treatment group. The 95% confidence intervals for median progression-free survival time will also be calculated for each treatment arm. The p-value for treatment effect will be generated using a stratified log rank test using platinum choice (cisplatin or carboplatin; see page 6) and prior treatment modality (WBRT or PCI) as stratification factors. The HR and its 95% confidence interval will be estimated using a Cox proportional hazards (PH) model with main effects for treatment and the aforementioned stratification factors.

According to the study design, administrations of randomized treatment (tarextumab or placebo only; without EP) may continue in 21-day cycles from the completion of 6 cycles of EP until the initiation of PCI. The following analysis of PFS will be conducted in order to determine if there is a treatment benefit when tarextumab is administered in combination with EP. Subjects who have not progressed will have their PFS censored 35 days (the scheduled time for 1 treatment cycle plus 7 days) following the last dose of Carboplatin/Cisplatin or EP. KM and Cox PH analyses will be the same as those described above.

The impact of the biomarkers Notch3, Hes1, Hey2, Hey1 and Hes6 on PFS will be evaluated with a Cox PH model with treatment, biomarker and treatment-by-biomarker interaction included in the model as independent variables. A separate Cox PH model will be used for each biomarker.

Sensitivity analyses for PFS include replicating the primary log-rank analysis using the PP population and unstratified log-rank tests using the ITT and PP populations.

The planned timing for the primary analysis of PFS is stated in section 5.5 above.

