3.1. Blinded Treatment Phase

Subjects who qualify for enrollment into the phase-2 portion of the study will be randomized in a 1:1 ratio to receive study treatment of EP with placebo or EP with tarextumab. The randomization will be balanced on the choice of platinum therapy (cisplatin versus carboplatin) and the prior use of whole brain radiation (WBR) or prophylactic cranial irradiation (PCI). Changing the choice of platinum therapy is not permitted once the subject is randomized. Treatment for each subject will begin on Cycle 1, Day 1 (the first dosing day). Etoposide 100 mg/m² will be given on Days 1, 2 and 3 and cisplatin 75 mg/m² or carboplatin to an AUC of 5 mg/mL/min will be given on Day 1 of every 21-day cycle for 6 cycles. Subjects may remain in the blinded treatment phase to continue one of the chemotherapy drugs if the other is held or discontinued prior to completing 6 cycles of EP and prior to disease progression. For subjects who have study drug held or discontinued for tolerability reasons, EP chemotherapy should continue to the completion of 6 cycles. Subjects may continue study drug if one or both of the chemotherapy drugs is held or discontinued prior to completing 6 cycles of EP and prior to disease progression.

After the completion of 6 cycles of EP, subjects who do not have disease progression and have not had WBR or PCI prior to study entry and are good candidates for PCI according to the

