14.2.2.3	Progression-Free Survival During Combination Chemotherapy (ITT Population)
14.2.2.4	Progression-Free Survival During Combination Chemotherapy (Per-Protocol Population)
14.2.2.5	Progression-Free Survival – Impact of Biomarker Expression (ITT Population)
14.2.2.6	Progression-Free Survival – Impact of Biomarker Expression (Per-Protocol Population)
14.2.2.7	Progression-Free Survival – Impact of Notch3 Expression in Subjects with High/Low Notch Pathway Markers (ITT Population)
14.2.2.8	Progression-Free Survival – Impact of Notch3 Expression in Subjects with High/Low Notch Pathway Markers (Per-Protocol Population)
14.2.2.9	Progression-Free Survival – Sensitivity Analysis (Per-Protocol Population)
14.2.3	Landmark Survival
14.2.3.1	Landmark Survival at 180, 360, 540 and 720 Days (ITT Population)
14.2.3.2	Landmark Survival at 180, 360, 540 and 720 Days (Per-Protocol Population)
14.2.4	Tumor Length
14.2.4.1	Summary Assessment of Tumor Length (ITT Population)
14.2.4.2	Summary Assessment of Tumor Length (Per-Protocol Population)
14.2.4.3	Rate of Change in Total Tumor Length at Progression (ITT Population)
14.2.4.4	Rate of Change in Total Tumor Length at Progression (Per-Protocol Population)
14.2.4.5	Rate of Change from Total Tumor Length at Baseline (ITT Population)
14.2.4.6	Rate of Change from Total Tumor Length at Baseline (Per-Protocol Population)
14.2.5	Best Overall Tumor Response
14.2.5.1	Best Overall Tumor Response Based on Investigator Assessment (ITT Population)
14.2.5.2	Best Overall Tumor Response Based on Investigator Assessment (Per-Protocol Population)
14.2.5.3	Best Overall Tumor Response Based on Investigator Assessment – Impact of Biomarker Expression (ITT Population)
14.2.5.4	Best Overall Tumor Response Based on Investigator Assessment – Impact of Biomarker Expression (Per-Protocol Population)
14.2.6	Duration of Response
14.2.6.1	Duration of Response (ITT Population)
14.2.6.2	Duration of Response (Per-Protocol Population)
14.2.7	Sites of Progression
14.2.7.1	Sites of Progression (ITT Population)
14.2.7.2	Sites of Progression (Per-Protocol Population)

Table Number	Table Description
14.3	SAFETY DATA
14.3.1	Displays of Adverse Events
14.3.1.1	Overall Summary of Treatment-Emergent Adverse Events (TEAEs) (Safety Population)
14.3.1.2	Treatment-Emergent Adverse Events (TEAEs) by System Organ Class and Preferred Term (Safety Population)

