Note: PFS= Date of Documentation of Death/Progression – Randomization Date + 1. Subjects who had not experienced death or progression by their last contact were censored at the time of their last radiographic response assessment. Subjects lacking a radiographic response assessment after randomization who do not progress or die have their event time censored on the date of randomization with duration of 1 day. For detailed event and censoring rules refer to protocol section 13.5.1 and SAP section 8.1. C.I. = Confidence Interval.

^[1] Sum of all individual follow-up times in days divided by 365.25.

^[2] The same censoring mechanisms used in the primary analysis of PFS were employed here. Additionally, for this analysis, a subject's PFS was censored 35 days (the scheduled time for 1 treatment cycle plus 7 days) following his or her last dose of etoposide or platinum.

^[3] Number of Subjects with Disease Progression or Death/ Total Follow-up Time (Person-years).

^[4] Hazard ratio and 95% C.I. from Cox proportional hazards model with main effects for treatment, platinum choice and prior treatment modality.

^[5] P-value for treatment effect from stratified log rank test using platinum choice and prior treatment modality as stratification factors.

Programmer notes: (a) repeat this table using the per-protocol population

Table 14.2.2.5
Progression-Free Survival – Impact of Biomarker Expression
ITT Population

Biomarker	Model Coefficients (SE) ^[1]		Hazard Ratio [95% Confidence Interval] ^[1]		
	Treatment x Biomarker Interaction		At 25 th Percentile	At 50 th Percentile	At 75 th Percentile
	Treatment	Interaction			
Notch3	xx.x (xx.x)	xx.x (xx.x)	xx.x [x.xx,xx.xx]	xx.x [x.xx,xx.xx]	xx.x [x.xx,xx.xx]
Hes1	xx.x (xx.x)	xx.x (xx.x)	xx.x [x.xx,xx.xx]	xx.x [x.xx,xx.xx]	xx.x [x.xx,xx.xx]
Hey2	xx.x (xx.x)	xx.x (xx.x)	xx.x [x.xx,xx.xx]	xx.x [x.xx,xx.xx]	xx.x [x.xx,xx.xx]
Hey1	xx.x (xx.x)	xx.x (xx.x)	xx.x [x.xx,xx.xx]	xx.x [x.xx,xx.xx]	xx.x [x.xx,xx.xx]
Hes6	xx.x (xx.x)	xx.x (xx.x)	xx.x [x.xx,xx.xx]	xx.x [x.xx,xx.xx]	xx.x [x.xx,xx.xx]

[1] Coefficients, hazard ratios and 95% confidence intervals are from Cox proportional hazards models with effects for treatment, biomarker and treatment-by-biomarker interaction. A separate model was used for each biomarker.

Programmer notes: (a) repeat this table using the per-protocol population

Table 14.2.2.7
Progression-Free Survival – Impact of Notch3 Expression in Subjects with High/Low Notch Pathway Markers
ITT Population

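### The section 8.1 rule for PFS during combination chemotherapy does not exclude events after the EP window and is worded differently from the footnote of its own table shell

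*SAP*

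**What the plan says.** Section 8.1 says this additional PFS analysis is done "in order to determine if there is a treatment benefit when tarextumab is administered in combination with EP". The rule comes next: "Subjects who have not progressed will have their PFS censored 35 days". The section counts those days from the final chemotherapy administration, which it words as "following the last dose of Carboplatin/Cisplatin or EP". Kaplan-Meier and Cox methods are otherwise those of the primary analysis. The primary event rules in the same section limit events by on-study assessments and by a 49-day limit for deaths. They set no limit tied to the end of EP.

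The shell of Table 14.2.2.3, whose title places PFS during combination chemotherapy, gives the rule again in footnote [2]. It first says "The same censoring mechanisms used in the primary analysis of PFS were employed here". Its second sentence adds a further rule, "a subject's PFS was censored 35 days (the scheduled time for 1 treatment cycle plus 7 days) following his or her last dose", where the dose meant is one of platinum or etoposide. The general note under the same table refers to section 8.1 for the detailed event and censoring rules.

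**The concern.** Taken at its word, section 8.1 treats two subjects on single-agent study drug differently according to what happens to them later. One who progresses at month 8 is an event at month 8. One who never progresses is censored a few weeks after the last EP dose. Beyond the window the risk set then holds only subjects who go on to have an event, and follow-up from the single-agent phase enters an estimate labelled as belonging to the combination phase.

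Footnote [2] carries no such restriction. Section 5.1 requires an independent programmer to validate the output. If one programmer follows section 8.1 and the other the shell, they could disagree on the status of a large share of the events, and a choice made after unblinding would be a choice between different hazard ratios.

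**Working it through.** **The plan's own figure.** Both places give a window of 35 days and describe it as one cycle plus 7 days. With the 21-day cycle of section 3.1, 21 + 7 = 28, so the 35 does not reproduce. The two statements need reconciling, but that is a separate matter from who is censored. I use 35 days as stated and 28 as a check.

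**Window end.** Platinum "will be given on Day 1 of every 21-day cycle for 6 cycles", so on schedule the last dose falls 5 × 21 = 105 days after Cycle 1 Day 1 (assumed to be the randomization date). The window ends at 105 + 35 = 140 days, and 140 / (365.25/12) = 4.60 months. Counting from etoposide on Day 3 gives 107 + 35 = 142 days, or 4.67 months.

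**Event-free at the window end** (Table 3 hazards):
- Control: exp(−0.1386 × 4.60) = 0.529.
- Treatment: exp(−0.0901 × 4.60) = 0.661.

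**Share of events by 18 months that fall after the window, w,** with no other censoring: [S(w) − S(18)] / [1 − S(18)]. Table 3 gives 0.0693 or 0.2310 per month beyond 8 months. I take 0.1386 (the late value in the title of Table 2) as the middle case.
- Control: S(18) = exp(−(0.6930 + 0.6932 + 0.6931 + 1.3860)) = 0.0313, and (0.5286 − 0.0313) / 0.9687 = 0.513.
- Treatment at HR 0.65: S(18) = exp(−0.65 × 3.4653) = 0.1051, and (0.6607 − 0.1051) / 0.8949 = 0.621.
- Over late hazards 0.0693 to 0.2310 and both dose anchors: 0.49-0.52 control and 0.59-0.64 treatment. With 28 days: 0.510-0.540 and 0.606-0.655.

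**Effect on the estimate.** Simulation, 300 trials per scenario, Cox model. Assumptions: 67 per arm (134 in Table 2), Table 3 hazards with 0.1386 beyond 8 months, random censoring at 0.40 × 0.1386 = 0.0554 per month in both arms, administrative censoring between 7 and 22 months, and the window ending at day 140 for everyone. The literal rule keeps every event and cuts subjects without an event to the window end, or to their last observation if earlier. The footnote rule stops everyone at the window end.

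| True effect | Primary HR | 8.1 literal HR | Footnote HR | Events, literal (after window) | Events, footnote |
|---|---|---|---|---|---|
| 0.65 up to window end, then 1 | 0.787 | 0.789 | 0.636 | 96.7 (48.3) | 48.3 |
| 1 up to window end, then 0.65 | 0.846 | 0.922 | 0.987 | 95.9 (39.0) | 56.9 |
| 0.65 throughout | 0.645 | 0.713 | 0.636 | 92.2 (43.9) | 48.4 |
| None | 0.999 | 0.992 | 1.002 | 99.3 (42.6) | 56.7 |

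The late share of counted events in these rows is 50%, 41%, 48% and 43%. Two larger runs of the same kind (2,000 trials per scenario) gave literal hazard ratios of 0.91 and 0.92 where the footnote rule gave 1.00, and 0.78 and 0.80 where it gave 0.64 and 0.65.

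**The case against.** The strongest reply is that there is only one rule, loosely worded. Censoring at a date ordinarily concerns subjects still event-free on that date, and both the stated purpose and the table title fit only that reading. The footnote marker sits on the row counting censored subjects, so the footnote need not be a different rule. This stands in part: a reader might infer that the plan has settled on counting late progressions, and the documents do not support that. The sentence is open to both readings. But the reader has to supply the missing qualifier, and the shell that hints at it defers to section 8.1.

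Two further stronger readings also fail.
- A reader might infer that non-progressors are moved forward to a date without a scan. Section 8.1 alone allows this, but footnote [2] retains the primary rules, including censoring at the last on-study assessment.
- A reader might infer a seriously inflated error rate. At one-sided 0.15, with an effect only after the window, the larger runs give 26-27% rejections against about 15% under the footnote rule. But section 4 attaches 0.15 to the main PFS and OS tests, and no section assigns it to this analysis. The default in section 5 is two-sided 0.05. There, with log(1/0.922) = 0.081 and standard error 2/√95.9 = 0.204, the shift is 0.40, and favourable rejections are roughly P(Z > 1.96 − 0.40) = 6% against 2.5%. With no effect in either phase the literal rule leaves the hazard ratio at about 1.

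**Conclusion.** The point holds as a wording defect with a material consequence if followed literally. Section 8.1 leaves the status of post-window events open, and the shell suggests the intended answer without settling it. Under the literal reading, about 40-50% of counted events lie outside the period being studied. The hazard ratio becomes about 0.92 instead of 1.00 when the effect comes only after the window, and about 0.79 instead of 0.65 when it comes only within it. These sizes assume the literal rule is programmed, EP runs on schedule, Table 3 hazards hold and the effect is confined to one phase. With a constant effect the shift is smaller (0.713 against 0.636). The primary PFS analysis and its power are unaffected, so this should be corrected but does not threaten the main conclusion.

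**What to change.** Replace the sentence in section 8.1 with wording that matches the shell, for example:

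> A progression or death that qualifies under the primary PFS rules and occurs on or before the window end is an event. Every other subject is censored at the earlier of the primary-analysis censoring date and the window end. A subject whose progression or death comes after the window end is censored at the window end and is not an event in this analysis.

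The event sentence must come first: a rule that simply censors all subjects at the earlier of two dates would, taken literally, also censor those who progressed inside the window. If the sponsor prefers to censor at the last on-study assessment on or before the window end, that should apply to every subject without an in-window event, so that the date does not depend on later outcome.

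Section 8.1 and footnote [2] should also state the same anchor. Neither says which last dose counts when platinum and etoposide stop on different dates, which section 3.1 allows.

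The cost is a few lines of text and no new data. The analysis will rest on fewer events, about 48-57 instead of 92-99 in the simulation.
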